9.1 Adverse events

Information about all clinically significant adverse events, whether volunteered by the subject, discovered by investigator questioning, or detected through physical examination, laboratory test or other means, will be collected and recorded and followed as appropriate. An adverse event is the appearance or worsening of any undesirable sign, symptom, or medical condition occurring

after starting the study drug even if the event is not considered to be related to study drug. Medical conditions/diseases present before starting study drug are only considered adverse events if they worsen after starting study drug. Abnormal laboratory values or test results constitute adverse events only if they induce clinical signs or symptoms, are considered clinically significant, or require therapy. Clinically significant laboratory results are those requiring a change in the patient's treatment, further diagnostic testing or specific clinical intervention (i.e., treatment delays or dose modifications, etc). The occurrence of adverse events should be sought by non-directive questioning of the patient at each visit during the study. Adverse events also may be detected when they are volunteered by the patient during or between visits or through physical examination, laboratory test, or other assessments. As far as possible, each adverse event should be evaluated to determine:

- the severity grade (mild, moderate, severe) or (grade 1-4)
- its relationship to the study drug(s) (suspected/not suspected)
- its duration (start and end dates or if continuing at final exam)
- action taken (no action taken; study drug dosage adjusted/temporarily interrupted; study drug permanently discontinued due to this adverse event; concomitant medication taken; non-drug therapy given; hospitalization/prolonged hospitalization)
- whether it constitutes a serious adverse event (SAE)

All adverse events should be treated appropriately. Such treatment may include changes in study drug treatment including possible interruption or discontinuation, starting or stopping concomitant treatments, changes in the frequency or nature of assessments, hospitalization, or any other medically required intervention. Once an adverse event is detected, it should be followed until its resolution, and assessment should be made at each visit (or more frequently, if necessary) of any changes in severity, the suspected relationship to the study drug, the interventions required to treat it, and the outcome.

Information about common side effects already known about the investigational drug can be found in the Investigator's Brochure or will be communicated between Investigator Brochure updates in the form of Investigator Notifications. This information will be included in the patient informed consent and should be discussed with the patient during the study as needed.

9.1.1 Attribution

Attribution is the relationship between an adverse event or serious adverse event and the study treatment. Attribution will be assigned as follows:

- Definite: The AE is clearly related to the study treatment;
- Probable: The AE is likely related to the study treatment;
- Possible: The AE may be related to the study treatment;
- Unlikely: The AE is doubtfully related to the study treatment;
- Unrelated: The AE is clearly not related to the study treatment.

9.2 Adverse Events of Special Interest (AESI)

Specific adverse events, or groups of adverse events, will be followed as part of standard safety monitoring activities. These events (regardless of seriousness) will be reported to Pharmacyclics Drug Safety per the SAE reporting timelines.

9.2.1 Major Hemorrhage

Major hemorrhage is defined as any of the following:

- Any treatment-emergent hemorrhagic adverse events of Grade 3 or higher*. Any treatment-emergent serious adverse events of bleeding of any grade
- Any treatment-emergent central nervous system hemorrhage/hematoma of any grade

*All hemorrhagic events requiring transfusion of red blood cells should be reported as grade 3 or higher AE per CTCAE vX.X.

Events meeting the definition of major hemorrhage will be captured as an event of special interest according to Section 11.4.6 above.

9.3 Serious adverse events

All serious adverse events and AESIs (initial and follow-up information) will be reported on FDA Medwatch (Form 3500A) or Suspect Adverse Event Report (CIOMS Form 1) IRB Reporting Form and sent via email ([contact]) or [contact]) to Pharmacyclics Drug Safety, or designee, within 24 hours of the event. Pharmacyclics may request follow-up and other additional information from the Sponsor Investigator.

All serious adverse events that have not resolved by the end of the study, or that have not resolved upon discontinuation of the subject's participation in the study, must be followed until any of the following occurs:

- The event resolves;
- The event stabilizes;
- The event returns to baseline, if a baseline value/status is available;
- The event can be attributed to agents other than the study drug or to factors unrelated to study conduct;
- It becomes unlikely that any additional information can be obtained (subject or health care practitioner refusal to provide additional information, lost to follow up after demonstration of due diligence with follow-up efforts).

9.3.1 SAE Definition

An SAE is any adverse event, without regard to causality, that is life-threatening or that results in any of the following outcomes: death; in-patient hospitalization or prolongation of existing hospitalization; persistent or significant disability or incapacity; or a congenital anomaly or birth defect. Any other medical event that, in the medical judgment of the principal investigator, may jeopardize the subject or may require medical or surgical intervention to prevent one of the outcomes listed above is also considered an SAE. A planned medical or surgical procedure is not, in itself, an SAE. Also specifically excluded from this definition of SAE is any event judged by the principal investigator to

represent progression of the malignancy under study, unless it results in death within the SAE Reporting Period.

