1.3.2 Ibrutinib clinical experience

As of 13 December 2013, 24 studies evaluating the safety, efficacy and pharmacokinetics (PK) of ibrutinib have been completed or are ongoing. These include 3 dose-finding Phase 1 studies, 5 studies in healthy volunteers, 7 Phase 2 studies using fixed continuous doses of ibrutinib, 1 Phase 1b study and 1 Phase 2 study combining ibrutinib with chemotherapy or immunotherapy, 5 randomized Phase 3 studies with 3 studies testing single-agent ibrutinib and 2 studies testing ibrutinib in combination, 1 extension study, and 1 extended-treatment rollover safety study for subjects who had participated in previous studies with ibrutinib. Across all studies, malignancies under investigation include chronic lymphocytic leukemia, small lymphocytic lymphoma, mantle-cell lymphoma, diffuse large B-cell lymphoma, follicular lymphoma, multiple myeloma, and Waldenstrom macroglobulinemia. Ibrutinib has never been tested in clinical trials evaluating patients with solid tumors.

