7.3 Confirmation Measurement/Duration of Response

Confirmation: To be assigned a status of PR or CR, changes in tumor measurements must be confirmed by repeat studies that should be performed no less than 4 weeks after the criteria for response are first met. In the case of SD, follow-up measurements must have met the SD criteria at least once after study entry at a minimum interval of 6 weeks. Progression of disease should be verified in cases where progression is equivocal. If repeat scans confirm PD, then progression should be declared using the date of the initial scan. If repeat scans do not confirm PD, then the subject is considered not to have progressive disease per RECIST 1.1.

Duration of Overall Response: The duration of overall response is measured from the time measurement criteria are met for CR/PR (whichever is first recorded) until the first date that recurrent or progressive disease is objectively documented (taking as reference for progressive disease the smallest measurements recorded since the treatment started).

The duration of overall complete response is measured from the time measurement criteria are first met for CR until the first date that recurrent disease is objectively documented.

Duration of Stable Disease: Stable disease is measured from the start of the treatment until the criteria for progression are met, taking as reference the smallest measurements recorded since the treatment started.

Progression Free Survival (PFS): PFS is defined as the time from the date of first study treatment to the date of the first documented disease progression or death due to any cause. If a patient has not progressed or died at the date of the analysis cut-off or when he/she receives any further anti-cancer therapy, PFS is censored at the time of the last tumor assessment before the cut-off or the anti-cancer therapy date.

Time to Treatment Failure: Time from administration of the initial dose of ibrutinib until study discontinuation for any reason (e.g. disease progression, toxicity, death, withdrawal of consent).

Biochemical marker response will be defined as $\geq 50\%$ reduction in tumor marker from baseline.

8. Statistical Considerations

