8.2 Endpoints to be followed

Efficacy Endpoints

- Tumor response rate using RECIST (Primary endpoint);
- OS, determined from the time of drug administration to death from any cause (Secondary endpoint);
- PFS, determined as the time from administration of the initial dose of ibrutinib until objective tumor progression using RECIST, or death (Secondary endpoint);
- Duration of response, defined as time from first observation of an objective response which is subsequently confirmed, to first disease progression or death due to any cause (Secondary endpoint);
- Changes in health-related quality of life, as assessed by EORTC questionnaires EORTC QLQ-C30 and QLQ GI.NET21 (see section 11).

Safety Endpoint

Safety assessments will consist of monitoring and recording all adverse events and serious adverse events, the regular monitoring of hematology and blood chemistry parameters and regular physical examinations. Adverse events will be evaluated continuously throughout the study. Safety and tolerability will be assessed according to the NIH/NCI Common Terminology Criteria for Adverse Events version 4 (CTCAE v4) available at: http://ctep.cancer.gov/protocolDevelopment/electronic_applications/ctc.htm. All adverse events will be documented on the adverse event CRF.

Exploratory Analyses (refer to Section 6.3)

As part of this study, we will explore the correlation between early biochemical response and response rates or PFS. Early biochemical responders will be defined as patients with elevated chromogranin A (CgA) who experience a major reduction (>50%) or normalization of their CgA between their baseline (pretreatment) measurement and their follow-up assessment 3 months later.

We also plan to undertake an exploratory analysis of blood- and tissue-based markers that may correlate with the clinical outcomes observed in the study. Exploratory markers will include the measurement of serum Tryptase- β 2 and the determination of the presence and activation of mast cells in the tumor tissue samples.

Archival pathology specimens will be reviewed at the study institution (Moffitt Cancer Center) for determination of mitotic rate (number of mitoses per 10 high-powered fields) and Ki-67 index.

This study is not sufficiently powered to establish definitive outcome for the correlative endpoints. These results will be considered hypothesis generating and any comparison with a significant alpha <0.05 will be deemed of sufficient interest to warrant further evaluation.

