9.3.2 SAE Reporting Period

The SAEs that are subject to this reporting provision are those that occur from after the first dose of the Study Drug through 30 days after discontinuation of the Study Drug.

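### Section 9.3.1 lets an undocumented judgement of progression remove an event from the SAE definition, unless it is fatal in the reporting period, and with it some serious low-grade bleeds from expedited reporting

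*Combined protocol and SAP*

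**What the plan says.** Section 9.3.1 opens broadly: "An SAE is any adverse event, without regard to causality", followed by the usual seriousness criteria. It closes with a carve-out: "Also specifically excluded from this definition of SAE is any event judged by the principal investigator to". What the judgement must find is that the event is progression of the study cancer; the one exception is an event that proves fatal inside the reporting period. Section 9.3.2 sets that period: SAEs are "those that occur from after the first dose of the Study Drug through 30 days after discontinuation of the Study Drug". No imaging or RECIST condition is attached to the judgement.

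Elsewhere the protocol keeps two kinds of progression apart. Section 5.4 lists documented progression and symptomatic tumor progression as separate grounds for removal, and asks for efforts to image in the symptomatic case. Section 7.1.5 has a separate label, symptomatic deterioration, for decline that ends treatment without objective evidence of progression.

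Three sets of rules depend on SAE status:
- Sections 9.3 and 9.5: the 24-hour report to the drug supplier, the protocol chair's report to the FDA and IRB, and the SAE follow-up rule.
- Section 6.2: at least monthly follow-up of grade 4 or serious events still ongoing when the drug is stopped.
- Section 9.2.1: one limb of major hemorrhage, an adverse event of special interest (AESI), is "Any treatment-emergent serious adverse events of bleeding of any grade".

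**The concern.** The carve-out brings a causal judgement into a definition that is meant to be free of one. The protocol already records causality separately, through the five attribution levels in Section 9.1.1, so seriousness need not carry that information as well.

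The setting makes the judgement hard to check. The trial is open-label, both cohorts receive the same drug, and there is no control group against which to compare serious events. The protocol states: "Ibrutinib has never been tested in clinical trials evaluating patients with solid tumors". Inclusion criterion 4 requires recent progression, so progression is a plausible explanation for a serious event in any patient. Section 1.3.3.4 names major gastrointestinal bleeding, some of it fatal, as a known risk of the drug, and bleeding can also be put down to tumor. Safety is a secondary objective (Section 2), and SAEs are part of the safety endpoint in Section 8.2. At stake are the completeness of the SAE count and the speed of reporting.

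**Working it through.** The plan gives no figure on this point, so none can be reproduced. The check is mainly a comparison of rules.

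**Step 1. What happens to the event.** Take a hospital admission that the investigator attributes to progression, with no qualifying scan and no death in the reporting period.

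| Rule | Section | Still applies? |
|---|---|---|
| Recorded as an AE, with hospitalization noted as action taken | 9.1 | Yes |
| Followed until it resolves, assessed at each visit | 9.1 | Yes |
| Reported to protocol chair and IRB under local policy | 9.5 | Yes |
| Monthly follow-up if drug was interrupted or stopped for an AE | Table 6-5, note b | Yes |
| Monthly follow-up of grade 4 events ongoing at discontinuation | 6.2 | Yes |
| Monthly follow-up of serious events below grade 4 ongoing at discontinuation | 6.2 | No |
| Classified as serious | 9.3.1 | No |
| 24-hour report to the drug supplier | 9.3 | No, unless an AESI |
| Chair's SAE report to the FDA | 9.5 | No |
| SAE-specific follow-up | 9.3 | No |

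Nothing in the protocol returns the event to SAE reporting if a later scan fails to show progression. Scheduled scans are every 3 cycles (12 weeks), so an event may well fall between two of them.

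**Step 2. Bleeding.** Section 9.2 sends AESIs to the supplier on SAE timelines whether or not they are serious. Under 9.2.1 a bleed qualifies if it is (a) grade 3 or higher, with any bleed needing red-cell transfusion counted there, (b) a serious bleeding event of any grade, or (c) in the central nervous system. Limb (b) takes its meaning from 9.3.1. A bleed that is serious, grade 1-2, outside the CNS, untransfused and judged to be progression fails (a) and (c) on its facts and (b) by the carve-out. It then has neither the SAE nor the AESI route.

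**Step 3. Size, as an illustration only.** Assume a type of serious event *not* due to progression with true rate p per patient, and a share k of such events wrongly called progression. Take n = 51 (Sections 4.3 and 8.1). Then

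P(at least one recorded as an SAE) = 1 − (1 − p(1 − k))^51.

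| p | k | p(1 − k) | Probability |
|---|---|---|---|
| 5% | 0 | 5.0% | 92.7% |
| 5% | 30% | 3.5% | 83.7% |
| 5% | 50% | 2.5% | 72.5% |
| 5% | 70% | 1.5% | 53.7% |
| 3% | 0 | 3.0% | 78.8% |
| 3% | 50% | 1.5% | 53.7% |

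In expected counts, at p = 5% and k = 50%, 51 × 0.05 = 2.55 such events become 51 × 0.025 = 1.275 recorded SAEs. Both p and k are assumed; the documents supply neither.

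**The case against.** Excluding progression from SAEs is a legitimate design choice, openly stated, and deaths in the reporting period are kept. That stands: the weakness is the missing documentation requirement, not the exclusion itself.

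The bleeding gap is narrow, since grade 3 or higher, CNS and transfused bleeds all stay reportable. That stands too. The illustration rests on assumed rates, and Section 8 attaches no toxicity boundary to seeing one SAE, so the probabilities drive no decision in the plan. Events correctly judged to be progression are not lost signal; only misjudged ones bias the count.

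A reader might infer several stronger things that the documents do not support:
- *Follow-up is lost.* Section 9.1 follows every AE until it resolves. Only the SAE-specific rules lapse.
- *The judgement decides what oversight bodies see.* Section 9.5 sends all AEs to the chair and IRB under local policy, the monitoring committees in 13.3 review safety and AE reporting, and 13.4 provides for source verification. Classification and speed change; the event is not hidden.
- *Progression means RECIST progression everywhere else.* Section 5.4 recognises symptomatic progression as a ground for removal.
- *The event also drops out of PFS.* Section 8.2 counts time "until objective tumor progression using RECIST, or death", and Section 7.3 runs to "the date of the first documented disease progression or death due to any cause", so an undocumented event is not a PFS event when it occurs. But SAE status and PFS serve different purposes, and being neither is not in itself an error. Sections 5.4 and 7.1.5 ask for efforts to image, Table 6-5 schedules an end-of-treatment scan, and later documented progression or death still counts unless new anti-cancer therapy comes first.

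**Conclusion.** The point holds as a limited one about safety classification and reporting. A judgement with no documentation behind it can remove the serious label, the 24-hour supplier report, the FDA report and the SAE-specific follow-up from an event that is not fatal in the reporting period. For one narrow class of serious bleeds it removes AESI reporting as well. SAE counts can be understated by the misjudged share. That share is unknown, and the figures above show only how the effect would scale under assumed rates. The events remain in the AE data, and the primary response test is untouched. The change is worth making because it is cheap and there is no control group to expose a misjudgement.

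**What to change.** 1. In 9.3.1, limit the exclusion to progression documented under Section 7.1. An otherwise serious event attributed to progression is reported as an SAE until progression is documented, and may be reclassified afterwards.
2. State that the exclusion does not apply to hemorrhage when 9.2.1 is applied.
3. List every event excluded under the clause, and present SAE rates with and without them. These events are already recorded as AEs under 9.1.

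The cost is short wording in 9.3.1, a few more SAE forms and one listing, with no added scan or visit. One limit remains: a scan shows that the tumor grew, not that growth caused the event. A drug-related event other than hemorrhage in a patient with documented progression could still be excluded, and the listing in item 3 is what keeps it in view.

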9.3.2 SAE Reporting Period

The SAEs that are subject to this reporting provision are those that occur from after the first dose of the Study Drug through 30 days after discontinuation of the Study Drug.

9.4 Pregnancy

Any pregnancy that occurs during study participation should be reported. To ensure patient safety each pregnancy must also be reported to Pharmacyclics within 24 hours of learning of its occurrence. The pregnancy should be followed up to determine outcome, including spontaneous or voluntary termination, details of birth, and the presence or absence of any birth defects, congenital abnormalities or maternal and newborn complications.

9.5 Data safety monitoring plan

Data including adverse events will be entered into Oncore. The participating investigator will report all adverse events to the protocol chair and to the IRB according to the local IRB's policies and procedures in reporting adverse events. The protocol chair has the obligation to report all SAE to the FDA and IRB. SAE and AESI will be also reported to Pharmacyclics Drug Safety per the SAE reporting timelines.

10. Data collection

Once eligibility has been established and the participant successfully registered, the participant is assigned a protocol case number. This number is unique to the participant on this trial and must be used for case report form (CRF) completion in Oncore.

Investigators must enter the information required by the protocol onto CRFs.

11. Quality of Life Assessment

Patient quality of life will be measured using the EORTC QLQ-C30 (version 3) and the EORTC QLQ GI.NET21 questionnaires (appendices B and C). The EORTC QLQ-C30 questionnaire is designed to assess the health-related quality of life of cancer patients participating in clinical trials. It is composed of 5 functional scales, three symptom scales, a global health status scale, and six single items. The EORTC QLQ GI.NET21 questionnaire is designed to assess physical and psychological symptoms related to neuroendocrine tumors of the gastrointestinal tract.

Both questionnaires will be scored and handled as recommended in the user manual. Missing items will be imputed with the mean of the non-missing items scored at that assessment time point. Ambiguous items will be considered as missing items. At each assessment time point, summary statistics of the raw score and linear transformation score (on a 0-100 scale) will be provided.

12. Publication of trial results

Publications resulting from this trial may be developed by the investigator who will provide Pharmacyclics an opportunity (within 30 days before submission or other public disclosure) to prospectively review any proposed publication, abstract or other type of disclosure that reports the results of the study.

13. Regulatory considerations

13.1 Protocol review and amendments

This protocol, the proposed informed consent and all forms of participant information related to the study (e.g., advertisements used to recruit participants) and any other necessary documents must be submitted, reviewed and approved by a properly constituted IRB governing the study location.

Any change or addition (excluding administrative) to the study protocol or informed consent form protocol must be submitted as amendments and must be reviewed and approved by Pharmacyclics prior to submission to the IRB and the investigator before implementation. Amendments significantly affecting the safety of subjects, the scope of the investigation or the scientific quality of the study require additional approval by the IRB. Any changes in study conduct must be reported to the IRB. The Principal Investigator will disseminate protocol amendment information to all participating investigators.

All decisions of the IRB concerning the conduct of the study must be made in writing.

